### Evaluation of best overall response

The best overall response is the best response recorded from the start of the study treatment until disease progression/recurrence (taking as reference for PD the smallest measurements recorded since the start of study treatment). The participant's best response assignment will depend on the achievement of both measurement and confirmation criteria (defined below).

Target Lesions	Nontarget Lesions	New Lesions	Overall Response
CR	CR	No	CR
CR	Non-CR/non-PD	No	PR
CR	Not evaluated	No	PR
PR	Non-PD or not all evaluated	No	PR
SD	Non-PD or not all evaluated	No	SD
Not all evaluated	Non-PD	No	NE
PD	Any	Yes or No	PD
Any	PD	Yes or No	PD
Any	Any	Yes	PD

CR=Complete Response; NE=Not Evaluable; PD=Progressive Disease; PR=Partial Response; SD=Stable Disease.

Participants with a global deterioration of health status requiring discontinuation of study treatment without objective evidence of disease progression at that time will be classified as

having “symptomatic deterioration”. Every effort should be made to document the objective progression even after discontinuation of treatment.

## Confirmation

- **Confirmation of response:**
  - The main goal of confirmation of objective response is to avoid overestimating the response rate observed. In cases where confirmation of response is not feasible, it should be made clear when reporting the outcome of such studies that the responses are not confirmed.
  - To be assigned a status of PR or CR, changes in tumor measurements must be confirmed by repeat assessments that will be performed no less than 4 weeks after the criteria for response are first met.
- **Confirmation of SD:** in the case of SD, follow-up measurements must have met the SD criteria at least once after study entry (signing of Informed Consent Form [ICF]) at a minimum interval of 8 weeks.

## Duration of overall response

- The duration of overall response is measured from the time measurement criteria are met for CR or PR (whichever status is recorded first) until the first date that recurrence or PD is objectively documented, taking as reference for PD the smallest measurements recorded since the treatment started.

## Duration of stable disease

- SD is measured from the start of the treatment until the criteria for disease progression are met, taking as reference the smallest measurements recorded since the treatment started.

## APPENDIX 4. SAFETY ASSESSMENTS

### A4-1. CLINICAL LABORATORY TESTS

The tests detailed in [Table 14](#) will be performed by the local laboratory with the exception of follicle-stimulating hormone (FSH), luteinizing hormone (LH), estradiol, progesterone, Inhibin A, Inhibin B, Anti-Müllerian hormone/Müllerian inhibiting substance, and CA-125, which will be sent to a central laboratory.

Protocol-specific requirements for inclusion or exclusion of participants are detailed in [Section 7](#) of the protocol.

Additional tests may be performed at any time during the study as determined necessary by the Investigator or required by local regulations.

Pregnancy testing (urine as described in the SoA [Schedule of Assessments]; [Section 1.3](#)) will be conducted at monthly intervals for WOCBP.

Serum pregnancy tests may be conducted in place of urine pregnancy tests throughout the study if required by local regulations.

Additional serum or urine pregnancy tests may be performed, as determined necessary by the Investigator or required by local regulation, to establish the absence of pregnancy at any time during the participant's participation in the study.

Investigators must document their review of each laboratory report.

**Table 14: Protocol-Required Laboratory Assessments**

Laboratory assessments	Parameters
Hematology	Platelet count Hemoglobin Hematocrit Red blood cell count Red blood cell indices: 
 
Mean cell volume
 
Mean cell hemoglobin
 
 White blood cell count with differential  : 
 
Neutrophils
 
Lymphocytes
 
Monocytes
 
Eosinophils
 
Basophils
 

Clinical Chemistry	Blood urea nitrogen Potassium Total and direct bilirubin Creatinine Sodium Aspartate Aminotransferase (AST) or Serum Glutamic-Oxaloacetic Transaminase (SGOT) Alanine Aminotransferase (ALT) or Serum Glutamic-Pyruvic Transaminase (SGPT) Gamma-glutamyl transferase Total protein Albumin Chloride Bicarbonate Glucose (non-fasting) Calcium Magnesium Inorganic phosphorous Estimated glomerular filtration rate (eGFR)  Uric acid Alkaline phosphatase

Laboratory assessments	Parameters
Routine Urinalysis	Specific gravity
	potential hydrogen (pH), glucose, protein, blood, ketones, bilirubin, urobilinogen, nitrite, leukocyte esterase by dipstick
	Microscopic examination (if blood or protein is abnormal) 
Other Tests	
Serology
 
 
• HIV antibody
 
• HBV 
 
◦ HBsAg
 
 
 
• HCV 
 
◦ Hepatitis antibody (HCV PCR if hepatitis C antibody positive)
 
 
 
 
Hormone Levels
 
 
• FSH
 
• LH
 
• Estradiol
 
• Progesterone
 
 
Tumor Markers
 
 
• Inhibin A
 
• Inhibin B
 
• AMH/Müllerian inhibiting substance
 
• CA-125
 

ALT = Alanine Aminotransferase; AMH = Anti-Müllerian Hormone; AST = Aspartate Aminotransferase; CA-125 = Cancer Antigen 125; FSH = Follicle-stimulating hormone; HBV = Hepatitis B virus; HBsAg = Hepatitis B surface antigen; HCV = Hepatitis C virus; HIV = Human immunodeficiency virus; LH = Luteinizing Hormone; PCR = Polymerase chain reaction; SGOT = Serum Glutamic-Oxaloacetic Transaminase; SGPT = Serum Glutamic-Pyruvic Transaminase

Manual microscopic review is performed only if white blood cell count and/or differential values are out of reference range.

Details of liver chemistry stopping criteria and required actions and follow-up assessments after liver stopping or monitoring event are given in [Section 9.1.1](#) and [Appendix A4-3](#).

Only required at Screening to establish eligibility and/or Baseline and permit full investigation of clinical observations on study. eGFR is calculated using the Chronic Kidney Disease Epidemiology Collaboration (CKD-EPI) equation. See [Appendix A4-5](#).

Microscopy examination is performed only if blood or protein is abnormal.

Serology only required at Screening

Participants reporting Adverse Events (AEs)/Adverse Events of Special Interest (AESIs)/Serious Adverse Events (SAEs) of reproductive system disorders will have hormone levels assessed every 3 months until event resolution (or for at least 90 days after discontinuing study treatment).

## A4-2. EASTERN COOPERATIVE ONCOLOGY GROUP PERFORMANCE

Grade	Description
0	Normal activity. Fully active, able to carry on all pre-disease performance without restriction
1	Symptoms, but ambulatory. Restricted in physically strenuous activity, but ambulatory and able to carry out work of a light or sedentary nature (e.g., light housework, office work)
2	In bed < 50% of the time. Ambulatory and capable of all self-care, but unable to carry out any work activities. Up and about more than 50% of waking hours
3	In bed > 50% of the time. Capable of only limited self-care, confined to bed or chair more than 50% of waking hours
4	100% bedridden. Completely disabled. Cannot carry on any self-care. Totally confined to bed or chair
5	Dead

Source: [\(Oken et al. 1982\)](#)

## A4-3. LIVER SAFETY: SUGGESTED ACTIONS AND FOLLOW-UP ASSESSMENTS

Liver Chemistry Stopping Criteria	
ALT-absolute	ALT $\geq$ 5 $\times$ ULN
ALT Increase	ALT $\geq$ 3 $\times$ ULN persists for $\geq$ 4 weeks
Bilirubin	ALT $\geq$ 3 $\times$ ULN and total bilirubin $\geq$ 2 $\times$ ULN ( $>$ 35% direct bilirubin)
INR^2	ALT $\geq$ 3 $\times$ ULN and International normalized ratio (INR) $>$ 1.5, if INR measured
Cannot Monitor	ALT $\geq$ 3 $\times$ ULN and cannot be monitored weekly for 4 weeks
Symptomatic	ALT $\geq$ 3 $\times$ ULN associated with symptoms (new or worsening) believed to be related to liver injury or hypersensitivity
Suggested Actions, Follow-up Assessments, and Monitoring	
Actions	

 
Immediately discontinue study treatment (nirogacestat)
 
Report the event to the Sponsor within 24 hours
 
Complete the liver event in the electronic Case Report Form (eCRF) and complete the SAE eCRF form if the event also met the criteria for an SAE
 
Perform liver chemistry follow-up assessments
 
Monitor the participant until liver chemistry test abnormalities resolve, stabilize, or return to baseline (see MONITORING)
 
Restart/rechallenge is not allowed per protocol and not granted, permanently discontinue study treatment and continue participant in the study for any protocol specified follow up assessments
 
	

Follow-Up Assessments	

• Viral hepatitis serology

• Obtain INR and recheck with each liver chemistry assessment until the transaminase values show downward trend

• Serum CPK and LDH

• Fractionate bilirubin, if total bilirubin <math>\geq 2 \times \text{ULN}</math>

• Obtain complete blood count with differential to assess eosinophilia

• Record the appearance or worsening of clinical symptoms of liver injury, or hypersensitivity, on the AE eCRF page

• Record use of concomitant medications (including acetaminophen, herbal remedies, and other over-the-counter medications) on the concomitant medications eCRF page

• Record alcohol use in the eCRF if AE is related to alcohol use

	

If <math>\text{ALT} \geq 3 \times \text{ULN}</math> AND <math>\text{bilirubin} \geq 2 \times \text{ULN}</math> or <math>\text{INR} > 1.5</math>:
 

• Anti-nuclear antibody, anti-smooth muscle antibody, Type 1 anti-liver kidney microsomal antibodies, and quantitative total Immunoglobulin G (IgG) or gamma globulins

• Serum acetaminophen adduct High performance liquid chromatography (HPLC) assay (quantifies potential acetaminophen contribution to liver injury in participants with definite or likely acetaminophen use in the preceding week (James, 2009)).

• Liver imaging (ultrasound, magnetic resonance, or computerized tomography) and/or liver biopsy to evaluate liver disease; complete liver

• Notify the medical monitor within 24 hours of learning of the abnormality to discuss participant safety

• Participant can continue study treatment

• Participant must return weekly for repeat liver chemistry tests (ALT, AST, alkaline phosphatase, bilirubin) until the abnormalities resolve, stabilize or return to baseline

• If at any time, the participant meets liver chemistry stopping criteria, proceed as described in Section 9.1.1

	

If, after 4 weeks of monitoring, <math>\text{ALT} < 3 \times \text{ULN}</math> and <math>\text{bilirubin} < 2 \times \text{ULN}</math>, monitor participants twice monthly until liver chemistry tests resolve, stabilize, or return to baseline
	
Monitoring	

If <math>\text{ALT} \geq 3 \times \text{ULN}</math> AND <math>\text{bilirubin} \geq 2 \times \text{ULN}</math> or <math>\text{INR} > 1.5</math>:
 

• Repeat liver chemistry tests (include ALT, AST, alkaline phosphatase, bilirubin and INR) and perform liver event follow-up assessments within 24 hours

• Monitor participant twice weekly until liver chemistry test abnormalities resolve, stabilize, or return to baseline

• A specialist or hepatology consultation is recommended

 
If <math>\text{ALT} \geq 3 \times \text{ULN}</math> AND <math>\text{bilirubin} < 2 \times \text{ULN}</math> and <math>\text{INR} \leq 1.5</math>:
 

• Repeat liver chemistry tests (include ALT, AST, alkaline phosphatase, bilirubin and INR) and perform liver chemistry follow-up assessments within 24 to 72 hours

• Monitor participants weekly until liver chemistry abnormalities resolve, stabilize, or return to baseline

 
<math>\text{ALT} \geq 3 \times \text{ULN}</math> and <math>< 5 \times \text{ULN}</math> and <math>\text{bilirubin} < 2 \times \text{ULN}</math>, without symptoms believed to be related to liver injury or hypersensitivity, and who can be monitored weekly for 4 weeks
	

AE = Adverse Event; ALT = Alanine aminotransferase; AST = Aspartate aminotransferase; CPK = Creatine phosphokinase; eCRF = electronic Case Report Form; HPLC = High Performance Liquid Chromatography; IgG = Immunoglobulin G; INR = International normalized ratio; LDH = Lactate dehydrogenase; SAE = Serious Adverse Event; ULN = Upper Limit of Normal;

Serum bilirubin fractionation should be performed if testing is available. If serum bilirubin fractionation is not immediately available, discontinue study treatment if  $\text{ALT} \geq 3 \times \text{ULN}$  and  $\text{bilirubin} \geq 2 \times \text{ULN}$ . Additionally, if serum bilirubin fractionation

testing is unavailable, record the absence/presence of detectable urinary bilirubin on dipstick which is indicative of direct bilirubin elevations suggesting liver injury.

 All events of ALT  $\geq 3 \times \text{ULN}$  and bilirubin  $\geq 2 \times \text{ULN}$  ( $> 35\%$  direct bilirubin) or ALT  $\geq 3 \times \text{ULN}$  and INR  $> 1.5$  may indicate severe liver injury (**possible 'Hy's Law'**) and must be reported as an SAE (excluding studies of hepatic impairment or cirrhosis). The INR stated threshold value will not apply to participants receiving anticoagulants.

 New or worsening symptoms believed to be related to liver injury (such as fatigue, nausea, vomiting, right upper quadrant pain or tenderness, or jaundice) or hypersensitivity (such as fever, rash or eosinophilia).

 Includes: Hepatitis A immunoglobulin M (IgM) antibody; hepatitis B surface antigen and hepatitis B core antibody; hepatitis C RNA; cytomegalovirus IgM antibody; Epstein-Barr viral capsid antigen IgM antibody (or if unavailable, heterophile antibody or monospot testing); and hepatitis E IgM antibody.

#### **A4-4. CORRECTED QT INTERVAL (QTC) PROLONGATION RISK**

Refer to the Study Reference Manual for a list of substances have been reported to show risk of QTc interval prolongation in published literature or have been demonstrated to have QT effects and risk of effect on cardiac repolarization in clinical studies.

#### **A4-5. CKD-EPI CREATNINE EQUATION**

Recommend use of calculator found at:

[https://www.kidney.org/professionals/kdoqi/gfr\\_calculator](https://www.kidney.org/professionals/kdoqi/gfr_calculator), which corresponds to the equation below.

Expressed as a single equation:

$\text{eGFR} = 142 * \min(\text{standardized } S_{\text{cr}}/K, 1)^\alpha * \max(\text{standardized } S_{\text{cr}}/K, 1)^{-1.200} * 0.9938^{\text{Age}} * 1.012$  [if female]

Source: [CKD-Epi Creatinine Equation, 2021](#)

##### **Abbreviations / Units:**

eGFR (estimated glomerular filtration rate) = mL/min/ 1.73 m^2

$S_{\text{cr}}$  (serum creatinine) = mg/dL

K = 0.7 (females) or 0.9 (males)

$\alpha$  = -0.241 (females) or -0.302 (males)

min = indicates the minimum of  $S_{\text{cr}}/K$  or 1

max = indicates the maximum of  $S_{\text{cr}}/K$  or 1

##### **Clinical Use:**

The Recommended method for estimating GFR in adults from the National Kidney Foundation is the 2021 CKD-EPI equations.

Designed for use with laboratory creatinine values that are standardized to IDMS. (See "About GFR" button.)

Estimates GFR from serum creatinine, age and sex

More accurate than the MDRD Study equation, particularly in people with higher levels of GFR.

The CKD-EPI equation is modeled using least squares linear regression to relate log transformed measured GFR to log-transformed filtration markers, age and sex with two slope splines for creatinine.

Some clinical laboratories are still reporting GFR estimates using the MDRD Study equation. The National Kidney Foundation has recommended that clinical laboratories should begin using the 2021 CKD-EPI equation to report estimated GFR using creatinine and cystatin C.

## **APPENDIX 5. ADVERSE EVENTS: DEFINITIONS AND PROCEDURES FOR RECORDING, EVALUATING, FOLLOW-UP, AND REPORTING**

### **A5-1. DEFINITIONS**

#### **A5-1.1. ADVERSE EVENT (AE)**

An Adverse Event (AE) is any untoward medical occurrence in a participant or clinical study participant, temporally associated with the use of study treatment, whether or not considered related to the study treatment.

An AE can therefore be any unfavorable and unintended sign (including an abnormal laboratory finding), symptom, or disease (new or exacerbated) temporally associated with the use of study treatment.

##### **Events meeting the AE definition:**

- Any abnormal laboratory test results (hematology, clinical chemistry, hormone levels, or urinalysis) or other safety assessments (e.g., electrocardiograms, radiological scans, vital signs measurements), including those that worsen from baseline, considered clinically significant in the medical and scientific judgment of the Investigator (i.e., not related to progression of underlying disease).
- Exacerbation of a chronic or intermittent pre-existing condition including either an increase in frequency and/or intensity of the condition.
- New conditions detected or diagnosed after study treatment administration even though it may have been present before the start of the study.
- Signs, symptoms, or the clinical sequelae of a suspected drug-drug interaction.
- Signs, symptoms, or the clinical sequelae of a suspected overdose of either study treatment or a concomitant medication. Overdose per se will not be reported as an AE/Serious Adverse Event (SAE) unless it is an intentional overdose taken with possible suicidal/self-harming intent. Such overdoses should be reported regardless of sequelae.
- "Lack of efficacy" or "failure of expected pharmacological action" per se will not be reported as an AE or SAE. Such instances will be captured in the efficacy assessments. However, the signs, symptoms, and/or clinical sequelae resulting from lack of efficacy will be reported as AE or SAE if they fulfil the definition of an AE or SAE.

**Events NOT meeting the AE definition:**

- Any clinically significant abnormal laboratory findings or other abnormal safety assessments which are associated with the underlying disease, unless judged by the Investigator to be more severe than expected for the participant's condition.
- The disease/disorder being studied or expected progression, signs, or symptoms of the disease/disorder being studied, unless more severe than expected for the participant's condition.
- Medical or surgical procedure (e.g., endoscopy, appendectomy): the condition that leads to the procedure is the AE. Any surgeries and/or procedures that were scheduled prior to obtaining the Informed Consent Form (ICF) but occurring afterwards will not be treated as an AE or SAE, unless the condition requiring the surgery or procedure worsened.
- Situations in which an untoward medical occurrence did not occur (social and/or convenience admission to a hospital).
- Anticipated day-to-day fluctuations of pre-existing disease(s) or condition(s) present or detected at the start of the study that do not worsen.

**A5-1.2. ADVERSE EVENTS OF SPECIAL INTEREST (AESI)**

Adverse Events of Special Interest (AESIs) are defined as non-serious or serious AEs that is one of scientific and/or medical concern specific to the Sponsor's product for which ongoing monitoring and rapid communication by the Investigator to the Sponsor can be appropriate.

**A5-1.3. SERIOUS ADVERSE EVENT (SAE)**

If an event is not an AE per definition in [Appendix A5-1.1](#), then it cannot be a Serious Adverse Event (SAE) even if serious conditions are met.

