#### Clinical Description and Presentation

OvGCTs originate from early ovarian mesenchyma and are composed of granulosa cells, theca cells, and fibroblasts.

Hyperestrogenism is reported in patients with OvGCT and is related to tumor production of estrogens, anti-Müllerian hormone (AMH), and inhibin A and B. This hormone production differentiates OvGCT from serous ovarian cancer and could serve as a tumor-specific pharmacodynamic marker.

A 2018 case series (Dridi et al. 2018), detailing 31 patients describes that sixty-one percent of cases presented with abdominal mass and/or abdominal pain, while postmenopausal bleeding was reported in 32% of cases. All cases underwent ultrasound imaging which showed mainly cystic unilateral masses in 80% of patients with a mean tumor size of 20cm (4-33cm).

Significantly elevated levels of CA-125 were reported in 42% of OvGCT patients.

Histologically, these tumors consisted of micro/macropollcules with cores “coffee bean” (74%), Call-Exner bodies (55%), and necrosis (22%) – mitotic index measured in only 22 patients was mainly low (64%). Local pelvic recurrence was seen in 70% of cases – only 9% of recurrences were abdominopelvic, 6% were retroperitoneal, 6% were pelvic and retroperitoneal, and 3% were abdominopelvic and retroperitoneal. Metastatic locations were mainly liver (67%) and pleura (33%).

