### **11.3.1. Adverse Events of Special Interest**

Adverse events of special interest (AESIs) are selected non-serious and serious AEs that must be reported regardless of relationship to study treatment.

Refer to [Table 9](#) for the AESIs identified for this study. AESIs will be followed until resolution or return to baseline.

Following medical evaluation, Sites may be contacted to provide supplemental information (such as medical history, concomitant medications, investigations, etc.) about the event. Please note this table lists known AESIs; additional events may be identified during the course of the study.

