**Table 9: Adverse Events of Special Interest (AESI)**

Skin Rash (reported as AESI if clinically significant Grade 2 and all Grade <math>\geq 3</math>. Per CTCAE v5.0)
Maculopapular rash
Pruritic rash
Erythematous rash
Folliculitis
Hidradenitis suppurativa
Elevated Liver Enzymes (reported as AESI if Grade <math>\geq 2</math>, per CTCAE v5.0)
AST
ALT
Alkaline Phosphatase
Total bilirubin
Electrolyte Insufficiency (reported as AESI if Grade <math>\geq 3</math>, per CTCAE v5.0)
Hypophosphatemia
Hypokalemia
Hypomagnesemia
Drug Reactions (reported as AESI for any grade)
Allergic reaction
Anaphylaxis
(Drug) hypersensitivity
Ovarian Toxicity (reported as AESI for any grade)
Ovarian dysfunction
Ovarian disorder
Amenorrhea
Oligomenorrhea
Premature menopause
Ovarian failure
Skin Cancer (reported as AESI for any grade)
Basal cell carcinoma
Squamous cell carcinoma (of skin)
Keratoacanthoma
Actinic keratosis
Any other skin cancer

AESI = Adverse Event of Special Interest; ALT = Alanine aminotransferase; AST = Aspartate aminotransferase; CTCAE = Common Terminology Criteria for Adverse Events

Participants reporting AEs/AESIs/SAEs of ovarian toxicity will have hormone levels assessed every 3 months until event resolution (or for at least 90 days after discontinuing study treatment).

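### A possible Hy's Law pattern attributed to the tumor must be an SAE under Appendix A4-3 but cannot be one under Appendix A5-1.3, and no rule says which prevails

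*Protocol*

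**What the plan says.** Two parts of the protocol decide whether a serious liver laboratory pattern is an SAE.

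- **Appendix A4-3, footnote 2.** All events of ALT ≥3×ULN with bilirubin ≥2×ULN (>35% direct), or of ALT ≥3×ULN with INR >1.5, are treated as possible severe liver injury and "must be reported as an SAE (excluding studies of hepatic impairment or cirrhosis"). The only other limit is that the INR threshold does not apply to participants on anticoagulants.
- **Appendix A5-1.1.** An abnormal laboratory result counts as an AE when it is "considered clinically significant in the medical and scientific judgment of the Investigator (i.e., not related to progression of underlying disease"). The list of events that are not AEs includes laboratory findings "which are associated with the underlying disease, unless judged by the Investigator to be more severe than expected for the participant's condition". Section 11.2.5 defines clinical significance in the same way.
- **Appendix A5-1.3.** If an event is not an AE, "then it cannot be a Serious Adverse Event (SAE) even if serious conditions are met".

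The A4-3 action list also calls for Sponsor notification within 24 hours and a liver-event eCRF entry for any liver stopping event. It makes the SAE form conditional on the event meeting SAE criteria, but that same line carries footnote 2. SAP 5.6.4 tabulates and lists participants who meet the liver stopping criteria, by cycle of onset and overall.

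**The concern.** Footnote 2 sets a laboratory rule that does not depend on suspected cause. Appendix A5 lets suspected cause decide, before anything is recorded, whether there is an AE at all. The protocol already has a later step for cause: in A5-2.2.2 the Investigator assesses causality for each recorded event and weighs underlying disease as an alternative. The A5-1.1 exclusion makes that judgment earlier, so the event may never reach that step.

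This matters because elevated transaminases are an important identified risk (Section 4.3), the trial has no control arm, and it has no Data Monitoring Committee (Section 12.4.1). A tumor explanation is plausible, since the case series in the Synopsis names liver as the leading metastatic location. Two sites with identical laboratory values could therefore file different reports, each following the protocol.

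**Working it through.** No figure in the plan bears on this point, so the check is to apply the rules to each case.

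| Case | A5-1.1 and A5-1.3 | A4-3 footnote 2 | Conflict? |
|---|---|---|---|
| Footnote 2 pattern, not attributed to the tumor | Not barred from being an AE or SAE | Must be an SAE | No |
| Footnote 2 pattern, attributed to the tumor, judged worse than expected | AE through the exception clause, so not barred | Must be an SAE | No |
| Footnote 2 pattern, attributed to the tumor, judged as expected | Not an AE, so cannot be an SAE | Must be an SAE | **Yes** |
| Isolated Grade ≥2 ALT rise, attributed to the tumor, judged as expected | Not an AE | Does not apply | No |

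Only the third row conflicts. No section states an order of precedence. The conditional SAE-form line in A4-3 does not settle it, because its own footnote says these patterns must be SAEs.

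Next, follow a third-row event that is handled under A5-1.3.

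- **Kept:** the 24-hour Sponsor notification and liver-event eCRF entry (A4-3), and the liver stopping-criteria table and listing, laboratory shift tables and Grade ≥3 listing (SAP 5.6.4). None of these needs an AE record.
- **Lost:** the AE/SAE record; the causality assessment (A5-2.2.2); evaluation as a serious adverse reaction or SUSAR, since A5-1.5 defines both from an SAE; the TEAE and serious-TEAE tables (SAP 5.6.2); and the hepatotoxicity table, which is built from preferred terms of recorded AEs (SAP 5.6.3 and 8.4.1.3).

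The size can only be illustrated. Take the 53 participants that SAP 5.8 gives as enrolled, assume all were treated, and use the Clopper-Pearson interval.

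- No case recorded: 0/53. Upper limit = 1 − 0.025^(1/53) = 6.72%, so the interval is 0–6.7%.
- One case recorded: 1/53 = 1.9%. Lower limit = 1 − 0.975^(1/53) = 0.05%. The upper limit solves (1−p)^53 + 53p(1−p)^52 = 0.025, giving p = 10.07%. The interval is 0.05–10.1%.

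This contrast applies to the AE/SAE record only. The laboratory-based table would count the participant either way.

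**The case against.** The best case on the other side is that the gap is narrow and the data survive. Entry requires AST/ALT ≤2×ULN and total bilirubin ≤1.5×ULN (with an exception for isolated elevation with direct bilirubin below 35%), and exclusion 5 bars known hepatic or biliary abnormalities. The Investigator would have to judge a new footnote 2 pattern as no worse than expected. Leaving disease-related findings out of AEs is also a coherent design choice. All of this stands and limits how often the conflict can arise. It does not remove it: liver lesions can appear on study, and footnote 2 makes no allowance for the Investigator's judgment.

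A reader might infer more than the documents support.

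- **That the event disappears.** It does not. It still reaches the Sponsor, the liver-event eCRF and the SAP 5.6.4 outputs.
- **That Section 11.3.1 and Table 9 form a second contradiction.** Section 11.3.1 covers AEs "that must be reported regardless of relationship to study treatment", which is not the same as whatever the cause, and A5-1.2 also defines AESIs as AEs. A finding that fails A5-1.1 is therefore not an AESI. Table 9 does not spell this out for tumor-attributed elevations, but silence is not conflict.
- **That amenorrhea raises the same problem.** SAP 8.4.1 says most participants will not menstruate and omits ovarian toxicity terms, and Section 4.2 describes amenorrhea as an initial manifestation, not as on-study progression.
- **That the 67% for liver is an expected rate.** It is a share of metastatic locations with no denominator given, in a 31-patient series where 70% of recurrences were local pelvic.

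**Conclusion.** The conflict is real and can be read directly from the text. For a footnote 2 pattern that the Investigator attributes to disease and judges as expected, A4-3 says it must be an SAE, A5-1.3 says it cannot be, and nothing says which governs. The consequence is confined to the AE/SAE record and what depends on it; Sponsor awareness and the laboratory outputs are unaffected.

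Its frequency is unknown and may be zero. On 53 treated participants, each affected case is 1.9 percentage points in the AE and SAE tables. The denominator is an assumption, because SAP 5.8 gives enrollment before a cutoff and does not give the final treated count. The point is worth correcting because it concerns an identified risk and costs little, not because it is likely to change the trial's overall safety conclusion.

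**What to change.** Reconcile A4-3 footnote 2 with A5-1.1 and A5-1.3. Add to both A5 sections that the exclusion for disease-related findings does not apply to the footnote 2 patterns; these are recorded as AEs and SAEs, with suspected tumor cause captured in the causality assessment.

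Before database lock, compare the ALT-with-bilirubin and ALT-with-INR participants on the SAP 5.6.4 list with the AE and SAE records, and query any without a matching record. The comparison should respect the footnote's anticoagulant exception for INR.

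The change should stop at the footnote 2 patterns. Making every Table 9 threshold an AE whatever the cause would be a wider trade-off that this conflict does not justify.

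The cost is one sentence in two appendix sections, one reconciliation listing, and possibly a few SAE reports that prove to be disease-related. No dosing or treatment-stopping rule is touched.
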